9.4.3 ANALYSIS OF THE SECONDARY ENDPOINT(S)

Secondary Endpoints
1. One-year cost-effectiveness of NewbornDx and rWGS compared with SOC testing, from a societal perspective
2. Lifetime year cost-effectiveness of NewbornDx and rWGS compared with SOC testing, from a societal perspective

We will conduct an economic evaluation that will compare costs and health outcomes for infants with suspected genetic disorders who undergo: 1) traditional standard of care diagnostic testing, 2) NewbornDx, or 3) rWGS. One-year post-identification outcomes for NewbornDx and rWGS will be estimated from trial data, while outcomes for standard of care will rely on retrospective chart review. We will use simulation modeling to extend our projections beyond 1-year post identification to a lifetime time horizon.

In Trial Data Collection for NewbornDx and rWGS:

This clinical trial provides a unique opportunity to examine observed health outcomes, care utilization, and family resource use for infants being evaluated for a suspected genetic disorder. During the trial, charge and cost data will be collected from the total hospital bill at discharge home from the index hospitalization in which the infant is enrolled in the study. Following discharge, the parent will be contacted every 30-days to collect resource utilization related to medical visits, hospitalizations, diagnostic tests, labs, procedures, and medications administered after discharge home until one year of age corrected for prematurity. Data will also be collected on: 1) mother and father lost work days; and 2) observed health outcomes, including death, diagnoses, and the timing of diagnosis. We will use a quality of life instrument to measure parental quality of life at monthly follow-up and to infer the value parents place on avoiding adverse health conditions. We will also collect parent-reported quality of life of the infant using a visual analog scale. Health economics practice guidelines call for inclusion of such outcomes, particularly in child health intervention evaluations^{59,60}.

Assessment of SOC testing

As no infant in our trial will only receive SOC testing only (i.e., without NewbornDx and rWGS), we will estimate standard of care testing outcomes (costs, diagnostic findings, health outcomes) by using a retrospective chart review.

In the retrospective chart review, we will collect resource utilization and health care outcome data from 300 infants born 12-18 months prior to the start of the study who had a genetic evaluation, but did not receive NewbornDx and rWGS. We chose infants born in this timeframe to minimize differences between contemporary clinical practice and clinical practice received by our retrospective cohort, hence maximizing the generalizability of our retrospective data to contemporary settings.

Simulation: Extending outcome estimates to a lifetime time horizon

Following data collection, we will use simulation modeling to estimate outcomes (cost, and health outcomes) for all strategies: NewbornDx, rWGS and standard of care diagnostic testing over a 1-year and lifetime horizon. For each strategy, the simulation model will project disorder progression based on estimated health state transition probabilities. By associating each health condition (or “health state”) with a “utility weight” (QALYs gained per year in that state) and annual cost, the simulation will track hypothetical infants and sum QALY gains and incurred costs. Repeating this process with a large number of simulated infants will yield estimated population health and cost outcomes. Costs and utility weights will be estimated from trial data, and previously published estimates, making the assumption that these values depend only on the infant’s health state and not on the diagnostic testing technology. Thus, we assume that the costs and utility weight estimates apply to infants undergoing any of the three diagnostic testing approaches.

Since NewbornDx and rWGS will identify a large number of disorders, disorders will be grouped based on estimated life expectancy and long-term severity. We will identify “disorder groups” by reviewing available data and literature on the expected outcomes of each identifiable disorder in conjunction with expert clinical judgment. We will also identify health states that appropriately represent the possible outcomes for each “disorder group” following review and synthesis of available evidence with input from our Steering Committee and DSMB.

Our lifetime simulation model will require: 1) classification of health states that describe health outcomes associated with each study strategy (e.g. disorder, disability, death); 2) health state transition probabilities, which represent the likelihood that simulated patients will develop specific disorder and disability outcomes, conditional on their assigned strategy; 3) health state costs, which include both health care associated with a specific health state and other societal costs; and 4) health state utilities, which represent health state preferences for avoiding adverse health outcomes. For the time period extending beyond the 1-year CGA trial duration, we will identify model transition probabilities, health state costs, and health utilities from existing primary datasets and the literature. For many genetic disorders, the literature reports limited long-term follow up data that appropriately account for expected differences in health outcomes due to differences in time to diagnosis. Available data will guide short-term extrapolation beyond our trial timeframe. For long-term time periods for which there are no informative data, we will draw on expert opinion, and conduct appropriate sensitivity analyses to characterize the impact of the attendant uncertainty. Health state costs will include the health care and societal costs (e.g. family costs, special education). We will estimate health care utilization, family time and other resources use for each health state from available data sources and then multiply these utilization estimates by national unit prices. We will also estimate child health state utilities using available data and will include utility values for parental quality of life when possible.

Cost-effectiveness analysis: With simulation findings corresponding to the 1-year CGA trial follow-up period and for extrapolation to a lifetime horizon, we will: 1) calculate

aggregate population costs and health outcomes (QALYs) for each trial strategy; 2) rank the strategies from least to greatest aggregate population health (total QALYs); and 3) calculate incremental QALYs and costs for the second strategy (compared to the first) and for the third strategy (compared to the second). Incremental QALYs are, by our sequencing of these comparisons, non-negative. If corresponding incremental costs are likewise non-negative, an incremental cost-effectiveness ratio (ICER) (incremental costs divided by incremental QALYs) will be calculated in a similar fashion. If incremental costs are negative in either case – that is, if either strategy reduces costs while improving health relative to its comparator – we refer to this strategy as “cost-saving”.

Secondary Endpoint	Definition	Scale	Populations for which the analysis will be conducted
Satisfaction of the web-based clinical reference database	Usefulness of information Ease of use of the clinical reference database	Categorical	Medical providers who use the clinical reference database after it is built

In order to qualitatively assess the impact of the intervention, we will collect surveys from medical providers across all sites. This survey will be submitted to the IRB prior to implementation.

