1 PROTOCOL SUMMARY

1.1 SYNOPSIS

Title:	Genomic Medicine for III Neonates and Infants (The GEMINI Study)
Study Intervention:	NewbornDx Sequencing Evaluation (NewbornDx), Rapid Whole Genome Sequencing (rWGS)
Study Description:	
This multicenter, prospective clinical trial will examine the diagnostic yield and clinical utility of NewbornDx and rWGS testing in high-risk infants with signs/symptoms consistent with a possible genetic disorder. Infants will undergo both NewbornDx and rWGS testing in parallel. Genetic sequences via NewbornDx and rWGS will be generated for the infant (proband) and when available, the biological parents, and analyzed. NewbornDx and rWGS test results will be returned to the infant's clinician, medical record and parent/guardian. Those infants analyzed as a duo or trio will have a retrospective analysis done of only the infant's data to determine if the same result would have been obtained with and without the parent samples. Clinical utility will be measured by clinician opinion and changes in the infant's care as a result of the genetic sequencing test results. Quality of life (QoL) and medical resource utilization by parent survey will be collected until the infant is one year corrected gestational age. These data, along with a retrospective chart review of infants with suspected genetic disorders, will be used to understand 1-year cost and health outcomes that would have been incurred in the absence of the advanced testing. The resulting data from the trial will be used in the economic evaluation comparing NewbornDx, rWGS, and SOC over a 1-year period and used as basis to simulate the lifetime cost-effectiveness of these testing strategies. A web-based clinical reference database to provide references, clinical management guidelines, opportunities for clinical trial participation, and support groups for each condition will be developed with separate interfaces for the parent/guardian(s) and medical provider. The clinical reference database will be qualitatively assessed by a survey of medical providers.

Objectives:	
• To estimate the diagnostic yield of NewbornDx and rWGS testing in identifying genetic disorders of unknown etiology• To assess the clinical utility of genomic sequencing

- To examine the economic impact and health outcomes of NewbornDx and rWGS in infants compared with SOC diagnostic testing, over a one-year and lifetime horizon

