When performed early in the clinical course, rWGS triples the diagnostic rate compared to SOC^{23, 24}. This provides preliminary evidence that rWGS or NewbornDx could be more cost effective and clinically useful than current standard of care (SOC)²⁵. Furthermore, data from the NSIGHT study (NCT02225522) indicates a diagnosis is made only 15% of the time in the neonatal period using SOC testing compared to 44% for rWGS⁷⁰. The total cost for clinical rWGS trio is ~ \$19,500,^{25,26} suggesting that NewbornDx panel followed by a reflex to rWGS (if necessary) may be a more optimal use of resources^{25,28-31}. Here we propose to examine the diagnostic yield of NewbornDx and rWGS, assess the clinical utility of genomic testing, and evaluate each technique's relative cost using data collected from the trial along with simulation modeling. The NIH, the National Academy of Medicine (NAM), and several European agencies have consistently identified scientific and operational barriers to implementation of genomic medicine. Specifically, the "burden to clinicians in obtaining, interpreting, and managing

results", including "integrating effective clinical decision support tools into the EMR" are some of the biggest challenges of scaling genomic medicine³²⁻³⁵.

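### The cost-effectiveness ranking leaves out NewbornDx with reflex to rWGS, a strategy the protocol's rationale raises, so it cannot show whether that strategy is efficient and may give rWGS the wrong comparator

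*Combined protocol and SAP*

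**What the plan says.** Section 2.1 (Study Rationale) puts a clinical rWGS trio at about $19,500, "suggesting that NewbornDx panel followed by a reflex to rWGS (if necessary) may be a more optimal use of resources". This is the only place where the protocol mentions a reflex strategy.

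Every description of the economic analysis names three strategies:

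- The synopsis (Section 1.1) plans an "economic evaluation comparing NewbornDx, rWGS, and SOC over a 1-year period", then a lifetime simulation of the same strategies.
- Section 9.4.3 compares infants "who undergo: 1) traditional standard of care diagnostic testing, 2) NewbornDx, or 3) rWGS".
- The simulation is "for all strategies: NewbornDx, rWGS and standard of care diagnostic testing over a 1-year and lifetime horizon", and it assumes that "costs and utility weight estimates apply to infants undergoing any of the three diagnostic testing approaches".
- The ICER procedure ranks strategies by total QALYs and computes increments "for the second strategy (compared to the first) and for the third strategy (compared to the second"). Two increments imply three strategies.

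The objectives (Section 3) and Hypothesis #2 (Section 4.1) also name only SOC, NewbornDx and rWGS. The sensitivity analyses in Section 9.4.3 address long-term inputs for which data are lacking, not additional strategies.

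**The concern.** In a sequential cost-effectiveness analysis, each strategy's ICER is taken against the next-ranked strategy. Leaving out a feasible option between two others changes the comparator for the higher one. Reflex testing is such an option. Counting an infant as diagnosed if either step is positive, it finds at least as many infants as rWGS, but panel-negative infants are diagnosed later. If it ranks between the panel and rWGS on QALYs, the ICER for rWGS should be taken against reflex, not against the panel alone. If reflex also costs more than rWGS for all, it drops out and the three-way ranking stands. The plan as written cannot tell these cases apart. The result is meant to inform adoption: Section 2.3.2 links wide uptake of NewbornDx to comparable yield and favourable cost-effectiveness.

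**Working it through.** The plan states no figure for a reflex strategy, so there is none to reproduce. The check asks when reflex would cost less than rWGS for all. It covers test cost only.

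**Inputs**

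- C, cost of rWGS: $19,500, a trio cost (Section 2.1).
- y, rWGS yield: 40% to 60%, the expected share of infants with a genetic diagnosis (Section 9.2). Section 2.1 cites 44% for rWGS, which lies inside this range.
- s, share of rWGS diagnoses found by the panel: at least 60% (Hypothesis #1, Section 4.1). Section 2.2 gives 85-94% in silico, as a share of variants, not of diagnoses.
- c, NewbornDx price: not given, so it is treated as unknown.

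Panel diagnoses are assumed to be nested within rWGS diagnoses. If the panel finds some that rWGS misses, reflex spares more rWGS tests and the break-even price rises.

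**Formulas**

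- Cost per infant, rWGS for all: C
- Cost per infant, reflex: c + (1 − y·s)·C
- Reflex is cheaper when c < y·s·C

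**Break-even NewbornDx price**

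| y | s | y·s | y·s × $19,500 |
|---|---|---|---|
| 0.40 | 0.60 | 0.240 | $4,680 |
| 0.44 | 0.60 | 0.264 | $5,148 |
| 0.50 | 0.60 | 0.300 | $5,850 |
| 0.60 | 0.60 | 0.360 | $7,020 |
| 0.50 | 0.85 | 0.425 | $8,288 |
| 0.60 | 0.94 | 0.564 | $10,998 |

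**Cost per extra diagnosis over NewbornDx alone, at y = 0.50 and s = 0.60**

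Extra diagnoses per infant: 0.50 − 0.30 = 0.20.

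- Reflex: (1 − 0.30) × 19,500 / 0.20 = 13,650 / 0.20 = $68,250, whatever c is.
- rWGS for all: (19,500 − c) / 0.20.

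| Assumed c | rWGS for all, per extra diagnosis | Reflex, per extra diagnosis | Reflex minus rWGS, per infant |
|---|---|---|---|
| $2,000 | $87,500 | $68,250 | −$3,850 |
| $4,000 | $77,500 | $68,250 | −$1,850 |
| $6,000 | $67,500 | $68,250 | +$150 |
| $8,000 | $57,500 | $68,250 | +$2,150 |
| $10,000 | $47,500 | $68,250 | +$4,150 |

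The order reverses at the break-even price of $5,850.

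**Infants affected by delay**

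Under reflex, the share who wait for a panel result before rWGS starts is 1 − y·s, from 1 − 0.564 = 43.6% to 1 − 0.240 = 76%. The diagnoses made only at the second step are y(1 − s), from 0.40 × 0.06 = 2.4 to 0.60 × 0.40 = 24 per 100 infants. Section 2.2 reports an average of 13 days to return NewbornDx results in preliminary work, so the delay need not be small.

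**Can the trial's data support a reflex arm?**

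- Every infant has both tests in parallel (Section 4.1), and the laboratories are blinded to each other's result until final results are returned (Section 6.1.1).
- Section 9.4.1 already estimates the proportions detected by one test and not the other.
- Section 9.4.2 defines time to result for each test, and the laboratory data listed with the Schedule of Activities include times of sample receipt and preliminary result.
- Section 9.4.3 already lets costs and utilities depend on health state alone, so they carry over to a fourth strategy.

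**The case against.** The strongest reply is that this is a matter of scope. The remark in Section 2.1 is hedged, and the protocol then says it will evaluate the relative cost of each technique. The objectives, Hypothesis #2 and the secondary endpoints all concern the two tests and SOC. No objective undertakes to find the best of all testing sequences, so the plan answers the question it sets. That stands, and it limits the weight of the point. It does not explain why a strategy raised in the rationale is missing from what Section 9.4.3 calls all strategies.

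A reader might infer that reflex is the likely efficient strategy. The documents do not support that. They say only that it may be, they give no panel price, and the order reverses within a plausible price range. The evaluation also rests on QALYs and societal cost, not test cost, and Section 2.1 stresses that diagnosis must come early to affect outcome.

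A reader might also infer that the trial will be unable to assess reflex at all. That is too strong as well: the clinical inputs are collected, and what is missing is pre-specification.

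Some technical objections also stand:

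- $19,500 is a trio cost, while infants may be tested without one or both parents (Section 5.2).
- Equal yield holds for the count of infants diagnosed, not for each infant's finding. NewbornDx does not detect structural variants (Section 6.1.1), and the laboratories may disagree.
- Suspicious VUS need a rule.
- Both clocks start at sample collection, so simply adding the two times is an assumption.

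That no infant will follow a reflex pathway is not decisive. No infant receives only NewbornDx or only rWGS either, so those arms must also be separated by modelling.

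**Conclusion.** The point holds as a gap in the pre-specified comparison. The three-way ranking cannot show whether the reflex strategy is efficient, and it may give rWGS an ICER against the wrong comparator. On test cost alone, reflex is cheaper than rWGS for all below a NewbornDx price of $4,680 to $10,998 and dearer above it. The upper end uses the in-silico share of variants. The range assumes rWGS at the trio cost and nested diagnoses, and it leaves out downstream cost, QALYs and delay. It therefore shows that the ranking could change, not in which direction. The point concerns a secondary objective; the primary yield, timing and utility endpoints are unaffected. It is a worthwhile, cheap improvement.

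**What to change.** Add a fourth modelled strategy to Section 9.4.3: NewbornDx first, then rWGS if NewbornDx gives no confirmed positive. This is an analysis scenario only; what infants receive in the trial does not change.

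- Build it from each infant's two results. Charge NewbornDx to all infants and rWGS to those without a confirmed panel positive.
- Use NewbornDx time for panel-positive infants. For reflexed infants, use NewbornDx time plus rWGS time.
- Include it in the one-year and lifetime rankings, and extend the ICER steps to four strategies.
- In sensitivity analysis, vary the overlap of collection and shipping time, the NewbornDx price, trio versus singleton rWGS cost, and the handling of suspicious VUS and discordant results.

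The cost is some wording and one more arm in the simulation, with no new patients or clinical data collection. The downside is that the reflex pathway and its delay are modelled, not observed.

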Site		Order rWGS (or Ultra Rapid for Urgent Cases) in the RCIGM portal; indicate secondary finding elections for infant and each biological parent		X						
Site		Complete Athena Laboratory requisition for NewbornDx, indicate infant secondary finding election		X						
Site		Notify Athena of need for urgent testing, if applicable		X						
Site		Ship samples to Athena Diagnostics and RCIGM (or Sema4*)		X						
Site		Scan redacted ICF signature pages into REDCap		X			X	X		
Site		Provide clinical information and HPO terms to RCIGM portal and Athena			X					
A		Complete NewbornDx [duo/trio if parent sample(s) are available]			X					
R		Complete rWGS [duo/trio if parent sample(s) are available]			X					
A, R		Return verbal provisional result, if applicable, with management guidance to enrolling site clinical staff*, site PI, study-wide Co-PI			X					
Site		Enter provisional result, if applicable, with management guidance as a research note to infant's medical record and notify the infant's parent/guardians			X					
A, R, S4		Complete confirmation testing for pathogenic, likely pathogenic and suspicious VUS findings*			X					
A, R, S4		Return final infant result to enrolling site research team and study-wide co-PIs/project manager				X				

A=Athena (Quest), R=RCIGM, S4=Sema4	Procedures	Screening	Enrollment	Genetic Sequencing	Return of final result	Transfer to facility	Discharge home	Follow-up #1-11	1 year CGA
R, S4	Return confirmed parental secondary findings to the enrolling site if applicable and the parent opted in on the ICF*			X					
Site	Return the final result for the infant to the clinical team, infant's medical record and the infant's parent/guardians			X					
Site	Notify the biological parent of confirmed secondary findings, if applicable and that parent opted in on ICF			X					
Tufts, Site	Follow adjudication procedures if the final results from NewbornDx and rWGS are discordant or if Sema4 does not confirm the rWGS result			X					
Site	Administer clinical utility survey				X				
Site	Obtain hospital bill(s) for infant hospitalization during which the research testing occurred				X	X			
Site	Obtain the parent/guardian contact information for follow-up				X	X			
Site	Administer parent SF-12 QoL and child visual analog scale					X	X	X	
Site	Administer or if completed by email, review the parent/guardian Resource Utilization monthly interview				X	X	X	X	
Site	Obtain medical records as necessary (i.e. a new diagnosis or adverse event)					X	X	X	

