5.4 STRATEGIES FOR RECRUITMENT AND RETENTION

The anticipated number of infants to be screened is approximately 1200 in order for 400 infants to complete the study. Six US sites will recruit for this study. The parent/guardian(s) of all eligible infants will be approached. Enrollment is expected to include about 50% of each sex and proportions of each race that are represented in the general population in the multiple sites where the studies will be performed. The entire ICF will be translated into Spanish and short forms in other non-English languages will be utilized.

This study involves monthly follow-up from discharge home until 1 year CGA. In order to reduce the risk of lost to follow-up, study staff will have the parent/guardian(s) fill out the Follow-up Contact Information form at the time of transfer or discharge home. This form will document several methods of contact for the parent/guardian(s) and a family member or friend who would know how to reach the parent/guardian(s) if their contact information changes or they are unreachable. Then, the study coordinators will contact the family monthly until 1 year CGA to complete the parent surveys/interviews.

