The following information from the infant's medical record entered into REDCap by staff at each enrolling site. Enrolling sites will have access to data entered into REDCap for infants at their own site. The study-wide co-PIs ([name]/[name]) and monitoring staff will have access to all data in REDCap.

Refer to the detailed grid of Data eCRFs in section 1.3 Schedule of Activities and the eCRF Instructions. Information collected and entered into the REDCap database for enrolled infants will include:

- identifiers (date of birth, date of hospital admission, dates of tests/procedures, parent email address if the parent wishes to complete follow-up surveys online – this email is not released or used outside of this study and will be removed when de-identifying the dataset)
- birth information (mode of delivery, birth weight, APGAR score, newborn screening results, pregnancy complications)
- phenotypic information (clinical symptoms, clinical presentations, HPO terms)
- clinical information (diagnoses, laboratory and imaging test results including clinical genetic testing results)
- clinical genetic tests that would have been done if this research study was not available
- genetic testing results as a result of study participation
- any actions because of the research genetic test results
- treatments (surgical procedures and medications)
- hospital billing information (CPT codes, billing data)
- medical visit, emergency room, hospitalization, procedures, treatments post discharge home
- quality-of-life assessments
- date and cause of death, if applicable
- adverse events

Data for this study will be collected at the following time points: at enrollment, following return of results, at time of an adverse event, at transfer, discharge home, withdrawal, or death and then monthly after discharge until the infant turns one-year CGA.

Upload of Source Documents to the REDCap System

Scanned source documents will be uploaded to the REDCap system for remote monitoring. Copies of medical records or source documents should be redacted of name and MRN or other account numbers, coded with the Infant Study ID, scanned to a PDF file and uploaded to REDCap.

Genomic Sequencing Results

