Upon the receipt of a report with a secondary finding for a biological parent by the site PI, the site will verify on the signed ICF that the biological parent opted-in to receive secondary findings. The result will be given to the biological parent by the enrolling site PI, study geneticist or genetics counselor and a referral to clinical genetics will be made. Some sites may opt to create a medical record for each biological parent and scan the consent and individual parental secondary findings to that medical record.

Genomic Sequencing Clinical Utility Survey

At discharge home or within one month after the return of results for infants who discharge home prior to the return of results, the physician of record at the time the results are returned will be asked to complete a brief survey regarding the clinical utility of the genomic testing. The one physician under whom the infant is admitted at the time results are received will receive the survey (i.e. neonatologist if the infant is in the NICU, pediatric critical care attending if the infant is in the PICU). The survey will be sent via email or a paper copy handed to the physician. The goal of the survey is to identify what changes were made to the immediate management of the infant as a result of testing as well as the general utility of the diagnosis. If the infant is discharged (home or death) prior to return of results, the Clinical Utility Survey should be completed by the clinical geneticist, most relevant subspecialist or by the site PI after speaking with the pediatrician (if baby was discharged home).

Parent/Guardian Contact Information, Medical Record Release and Diaries at Transfer/Discharge Home

The parent/guardian(s) will fill out a contact information form with multiple methods of contact to ensure we are able to reach the parent/guardian or primary care provider until the infant is 1 year CGA. A quality of life (QoL) instrument (The Optum™ SF-12v2® Health Survey) and the Child Visual Analog Scale will be administered.

Billing Information

At transfer to another facility and/or discharge home, the enrolling site research staff will obtain the final hospital costs and charges, and all physician CPT codes, for the infant's hospitalization.

Parent/Guardian Interview and Medical Record Acquisition

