Following transfer of facility or discharge home, study staff will contact one parent/guardian monthly to assess how the infant is progressing until 1 year CGA. The parent/guardian will be asked about any new testing, diagnosis, medications, medical visits or hospitalizations, and any missed days of work due to their child's disorder. Ideally, the parent will receive a link via email to complete the monthly parent survey online in the REDCap system; however, the parent/guardian may be contacted by e-mail or phone per the parent/guardian's preference. Self-reported QoL information will be collected from a parent/guardian at 3-month intervals to infer the impact on the family of any prolonged illness. The follow-up surveys will be translated into Spanish. In the case of a parent/guardian who does not read English or Spanish, the follow-up contact will need to be made with an interpreter by phone. Upon request by the health

economics analysts and as permitted in the ICF, medical records and billing information from any hospitalizations and any outpatient health care utilization may be obtained from the provider institutions to complement parent/guardian self-report.

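### Sections disagree on whether resource-use collection starts at transfer or at discharge home, so a transferred infant's receiving-hospital stay may be missing from the one-year costs

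*Combined protocol and SAP*

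**What the plan says.** **Start of resource-use collection**

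- Section 9.4.3 (in-trial data collection): parents are contacted every 30 days after discharge about visits, hospital stays, tests, procedures and "medications administered after discharge home until one year of age corrected for prematurity".
- Section 8.2, data entry into REDCap: the time points are "at transfer, discharge home, withdrawal, or death and then monthly after discharge until the infant turns one-year CGA", and the utilization item reads "medical visit, emergency room, hospitalization, procedures, treatments post discharge home".
- Section 8.2, parent interview: "Following transfer of facility or discharge home, study staff will contact one parent/guardian monthly". The interview asks about hospital stays.
- Section 5.4: "This study involves monthly follow-up from discharge home until 1 year CGA". The lines that follow have the contact form completed at transfer or discharge home, with monthly contact after that.

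**Hospital bill**

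- Section 9.4.3: "charge and cost data will be collected from the total hospital bill at discharge home from the index hospitalization in which the infant is enrolled".
- Schedule of Activities: "Obtain hospital bill(s) for infant hospitalization during which the research testing occurred".
- Section 8.2, billing: "At transfer to another facility and/or discharge home, the enrolling site research staff will obtain the final hospital costs and charges".
- Section 8.2, parent interview: records and bills from other institutions may be obtained if the health economics analysts ask for them and the consent form permits it.
- The eCRF submission schedule places the Hospital Bill and CPT forms in a single column for transfer and/or discharge home.

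**The concern.** Transfer and discharge home are separate events in this protocol: they have their own columns in the Schedule of Activities and are named separately in section 8.2. The wording difference therefore cannot be dismissed as two names for one event. A transferred infant has an interval of inpatient care between the two dates. The analysis section, which the health economists will work from, appears to leave that interval out of the parent-reported data, while the required bill is tied to the stay before it. Inpatient care is costly, so a gap there matters more than a missed clinic visit.

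At stake are the one-year cost-effectiveness endpoint and the health-state costs that section 9.4.3 takes partly from trial data for the simulation. Hypothesis #2 also compares cost with standard of care, whose outcomes come from a different source, the retrospective chart review.

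**Working it through.** The plan states no figure to reproduce. The check is a comparison of the sections, followed by the form of the error and an illustration.

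**1. Which sections start where**

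| Place | Start |
|---|---|
| 9.4.3 | after discharge, then discharge home |
| 8.2, REDCap data list | discharge home |
| 5.4, opening sentence | discharge home |
| 5.4, contact procedure | transfer or discharge home |
| 8.2, parent interview | transfer or discharge home |
| Schedule of Activities, resource-use row | transfer is marked |

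The Schedule row needs care, because its columns may have shifted when the PDF was read. It carries four marks. As extracted they fall at return of result, transfer, discharge home and follow-up. Moved one column, as the footnote on the SF-12 schedule suggests, they fall at transfer, discharge home, follow-up and 1 year CGA. Transfer is marked either way.

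**2. What is captured between transfer and discharge home**

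- Under the section 9.4.3 rule: the bill is for the index stay and the parent data begin at discharge home. The receiving-hospital stay is in neither.
- Under the parent-interview rule: the stay is asked about and can be supported by a bill, but only if the analysts request one.

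**3. Form of the error**

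Let D_T be the mean omitted cost per infant in the trial data and D_S the mean omitted cost per infant in the chart review.

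- Error in the absolute trial cost = −D_T.
- Error in the observed cost difference, trial strategy minus standard of care = D_S − D_T. This is zero if both sources treat transfers alike.
- NewbornDx minus rWGS: every infant receives both tests, so the same omission enters both sides and cancels in the observed costs.

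Section 9.4.3 also assumes that costs depend on health state and not on the testing technology. In the simulation, understated health-state costs are therefore carried into all three strategies.

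**4. Illustration, not an estimate**

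Omitted cost per enrolled infant = (share transferred) × (receiving-stay cost as a share of the average NICU cost) × $76,164. The last figure is from section 2.1. Both shares are assumptions, and the formula supposes that every such stay is lost.

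| Transferred (of 400) | Stay cost share | Omitted per enrolled infant |
|---|---|---|
| 5% (20) | 10% | 0.05 × 0.10 × 76,164 = $381 |
| 20% (80) | 25% | 0.20 × 0.25 × 76,164 = $3,808 |
| 30% (120) | 50% | 0.30 × 0.50 × 76,164 = $11,425 |

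These are 0.5%, 5% and 15% of $76,164. The 30-fold spread comes entirely from the assumed shares, so no single value should be relied on.

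**The case against.** The best defence is that the operational text is sound. The parent-interview procedure, the Schedule of Activities and the contact steps in section 5.4 all include transfer, so coordinators following them would ask about the receiving-hospital stay. Section 9.4.3 and the REDCap list are then loose summaries. In section 9.4.3 the discharge-home phrase may even attach to medications alone, and its total bill at discharge home might be read to span a transfer. Bills from any hospital can be requested. Section 9.4.3 also values utilization at national unit prices in costing health states, so a parent-reported stay could be costed without an outside bill.

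Much of this stands, and it is why the loss is possible rather than certain. It does not remove the conflict. The analysis section ties the bill to the index stay, section 8.2 allows that bill to be taken at transfer, and retrieval of other bills is discretionary. Sites and analysts could follow either rule.

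A reader might also infer two further faults from the forms, and neither is supported.

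- That no bill is due when an infant dies in hospital. Section 8.2 names death as a data time point and lists billing among the data collected. Only the form's column label omits it. Still being an inpatient at 1 year CGA does lack a named trigger.
- That the label Follow-up #1-11 caps the contacts below what preterm infants need. Sections 5.4 and 8.2 already require monthly contact until 1 year CGA, and nothing says that contact stops after the eleventh.

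**Conclusion.** The inconsistency is real and minor. Sections 9.4.3 and 8.2 (REDCap list) limit resource use to care after discharge home, while the parent-interview text of 8.2 starts at transfer or discharge home. If the former is followed, receiving-hospital stays fall outside both required sources. Absolute one-year costs and the trial-derived health-state costs would then be understated.

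The contrast with standard of care is biased only if the chart review captures transfers differently, and the documents do not say how it treats them. A reader might infer that the omission distorts NewbornDx against rWGS, or might set it beside the price of an rWGS trio. The documents do not support either: both tests are done in the same infants, health-state costs are shared, and a mostly shared omission is not comparable with a cost that differs between strategies.

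The size is unknown. The range of $381 to $11,425 per enrolled infant rests on assumed transfer rates, assumed stay costs and total loss of those stays.

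**What to change.** - Amend section 9.4.3, the REDCap list in section 8.2 and the opening sentence of the follow-up paragraph in section 5.4 to match the parent-interview text: collection starts at the first of transfer or discharge home and expressly includes the receiving-hospital stay.
- State in the billing text of section 8.2 and in section 9.4.3 that the receiving hospital's bill is requested for every transferred infant, under the release the consent form already permits. Where no bill can be had, value the parent-reported stay at unit prices.
- Apply the same transfer rule to the retrospective standard-of-care cohort and say so.
- In the eCRF schedule, name death as a time point for the Hospital Bill and CPT forms, in line with section 8.2, and add still being an inpatient at 1 year CGA.

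The cost is a wording amendment, small changes to form triggers and one records request per transferred infant. Some outside bills will be slow or unobtainable, so the rule for using the fallback should be written down before the cost analysis begins.
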